7.2 General Principles

All statistical analyses will be conducted using SAS[®] Version 9.4 (SAS Institute, Cary, NC).

For categorical variables, the count and proportions of each possible category value will be tabulated. The denominator for the proportion will be based on the number of subjects in the analysis sets. For continuous variables, the mean, median, SD, minimum, and maximum values will be presented for all patients in the relevant analysis set.

Means and medians will be presented to 1 more decimal place than the recorded data. The standard deviations (SDs) will be presented to 2 more decimal places than the recorded data. Minimum and maximum are presented using the same number of decimal places as the recorded data. Confidence intervals about a parameter estimate will be presented using the same number of decimal places as the parameter estimate.

All confidence intervals, statistical tests, and resulting P-values will be reported as 2-sided. P-values should be presented to 3 decimal places, with values less than 0.001 presented as <0.001.

Baseline values are defined as the last observed value before the first dose of the study drug. The summary tables will include escalation cohorts, overall for dose escalation phase, safety lead-in cohort in expansion phase, and by expansion cohorts and overall for expansion phase and overall for both phases as appropriate.

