4.3.2.2 Study 1001

Seventeen patients were enrolled in Study 1001 as of the data cutoff of 23 January 2021 for preliminary analysis. The majority were white (88.2%) and male (58.8%). Patients ranged from 42 to 80 years of age, with a median of 64.0 years. Median duration of treatment overall was 3.14 weeks, and median number of treatment cycles received was 2. The majority of patients (70.6%) have discontinued study drug treatment, and 3 patients (17.6%) have discontinued the study. The primary reason for treatment discontinuation was progressive disease (75.0%).

[figure not shown]
All 17 patients (100%) in the study have experienced a TEAE. The most common TEAE was infusion-related reaction, which was reported in 8 patients (47.1%). Six patients (35.3%) had a TEAE of nausea, and TEAEs of chills, headache, and thrombocytopenia were each reported in 5 patients (29.4%).

Ten patients (58.8%) experienced an SAE, the most common of which was IRR (7 patients, 41.2%). All TEAEs of IRR were considered related to study drug. The only other SAE reported in more than 1 patient was muscular weakness, which occurred in 2 patients (11.8%).

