7.2.3 Methods for Handling Missing Data

For efficacy and safety data, no imputation of values for missing data will be performed. Imputation rules for incomplete dates are described in Appendix B.

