7.3 Analysis Sets

- Safety Analysis Set: The safety analysis set will include all enrolled patients who received at least one dose (even incomplete) of the study drug.
- Response evaluable Analysis set: The response evaluable analysis set is a subset of the safety analysis set including patients with measurable disease at baseline and at least 1 post-treatment evaluation.
- DLT Evaluable Analysis Set: patients who receive all Cycle 1 doses of modakafusp alfa or experience a DLT in Cycle 1 in the dose-escalation portion of the study; or patients who receive all Cycle 1 doses of modakafusp alfa in combination with pembrolizumab or experience a DLT in Cycle 1 in the safety lead-in portion of the study.
- Pharmacokinetic Analysis Set: patients from the safety analysis set who have sufficient data to calculate at least 1 PK parameter for modakafusp alfa.
- Immunogenicity-evaluable Analysis Set: Includes patients with a baseline and at least one post-baseline immunogenicity assessment.

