7.11 Other Outcomes

7.11.1 Immunogenicity Analysis

The immunogenicity of modakafusp alfa will be assessed by determining anti-modakafusp alfa antibody incidence and characteristics (e.g., titer and specificity). All ADA data will be listed. For patients in the immunogenicity evaluable analysis set, percent of patients with positive ADA at each timepoint, as well as percent of patients with positive ADA by domain specific assay and ADA titers, will be summarized by dose levels by study phases (escalation and expansion). Percent of patients with positive ADA at baseline and at any post-baseline time point during the study will be reported. Additional summary tables and figures may be generated to assess the impact of anti-modakafusp alfa antibodies on the pharmacokinetic profile, drug efficacy, pharmacodynamic profile, and clinical safety will be evaluated, if possible. These analyses will be exploratory in nature and may be included in CSR if there is a trend.

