7.12.3 Vital Signs

Descriptive statistics for vital sign results (diastolic and systolic blood pressure, heart rate, pulse rate and body weight) will be summarized as follows:

- Baseline value (C1D1 or screening if C1D1 is not available).
- Minimum post-baseline value.
- Change to Minimum post-baseline value.
- Maximum post-baseline value.
- Change to Maximum post-baseline value.

Changes to the minimum and maximum post-baseline values will be calculated relative to the baseline value.

For blood pressure values collected during the infusion (every 30 minutes), the number and percentage of patients with changes from pre-infusion blood pressure values will be summarized in the following categories:

- Increase of diastolic blood pressure of at least 10 mm Hg during any infusion.
- Decrease of diastolic blood pressure of at least 10 mm Hg during any infusion.
- Increase of systolic blood pressure of at least 20 mm Hg during any infusion.
- Decrease of systolic blood pressure of at least 20 mm Hg during any infusion.

7.12.4 12-Lead ECGs

ECG data (ventricular rate, RR interval, PR interval, QT interval, and QTcF interval) will be summarized as follows:

- Baseline value (C1D1 or screening if C1D1 is not available).
- Minimum post-baseline value.
- Change to Minimum post-baseline value.
- Maximum post-baseline value.
- Change to Maximum post-baseline value.

Changes to the minimum and maximum post-baseline values will be calculated relative to the baseline value.

In addition, a categorical analysis of QTcF intervals will be performed for each time point. The number and percentage of patients in each QTcF interval (<450 msec, 450-480 msec, >480- <500 msec, and ≥ 500 msec) will be summarized at baseline and each of the subsequent time points. Categories of changes from baseline (≥ 30 msec and ≥ 60 msec) will be summarized as well.

[figure not shown]

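### SAP 7.2 bases every categorical percentage on the analysis-set size, so ADA-positive and QTcF percentages by time point are understated wherever results are missing

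*SAP*

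**What the plan says.** SAP 7.2 sets the general rule for categorical variables: "The denominator for the proportion will be based on the number of subjects in the analysis sets". No separate rule is given for summaries by visit.

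Two outputs by time point fall under it:

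- **ADA.** SAP 7.11.1 asks for "percent of patients with positive ADA at each timepoint", in the immunogenicity-evaluable set. SAP 7.3 defines that set as follows: "Includes patients with a baseline and at least one post-baseline immunogenicity assessment". Membership is settled once and does not depend on having a sample at each visit.
- **QTcF.** SAP 7.12.4 states that "a categorical analysis of QTcF intervals will be performed for each time point". It adds: "The number and percentage of patients in each QTcF interval" is tabulated over four ranges and "will be summarized at baseline and each of the subsequent time points". The section does not name its analysis set.

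On missing values, SAP 7.2.3 says: "For efficacy and safety data, no imputation of values for missing data will be performed". No category for missing results is defined for either table.

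The schedules of events (Protocol Appendix A) draw ADA samples before dosing on Day 1 of each cycle while the patient stays on treatment, and at end of treatment if possible. Local safety ECGs are scheduled at screening, C1D1, C2D1 and end of treatment in phase 1b, and additionally at C3D1 in phase 2. Time-matched triplicates are confined to C1D1 and C1D2, in dose escalation and the safety lead-in.

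**The concern.** A patient who has left treatment has no ADA sample at later cycles but remains in the immunogenicity-evaluable set. Under the rule as written, that patient stays in the denominator and cannot appear in the numerator. In the table this is indistinguishable from a negative result. The same happens to a patient with no ECG at a visit: counted in the denominator, present in none of the QTcF ranges.

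The percentage by time point then mixes two quantities: how common the finding is among patients assessed, and how many patients are still assessed. A constant ADA rate would be displayed as a declining one. SAP 7.11.1 specifies no table of transient versus persistent ADA, so these percentages are its main prespecified summary of ADA over time. At stake is whether two descriptive safety tables can be read correctly.

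**Working it through.** **Inputs from the documents**

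- Protocol 4.3.2.2, cutoff 23 January 2021: 17 patients enrolled, 70.6% off treatment, and "median number of treatment cycles received was 2".
- Protocol 4.3.3: 6 of 8 patients with ADA data were positive after treatment.

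**Reproducing the stated figures.** 6/8 = 75.0%. 12/17 = 70.6%, so 12 patients had stopped treatment and 5 of 17 (29.4%) were still on it.

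**How many reach later visits.** With 17 patients the median is the 9th ordered value. It equals 2, so at least 9 patients had received 2 cycles or fewer and at most 8 of 17 (47.1%) had started Cycle 3 by the cutoff. This count includes patients still on treatment who had not yet got that far, so it is not a dropout rate. It does show that later visits can hold far fewer patients than the set.

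**Formula.** Let N be the set size, n the number assessed at a time point, and p the proportion positive among those assessed.

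- SAP 7.2 as written: (p × n) / N = p × (n/N).
- Denominator of patients assessed: (p × n) / n = p.

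The two agree only when n = N.

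**ADA illustration.** Assume N = 25, the planned maximum per expansion cohort. Take n from fractions assessed of 75% (assumed), 8/17 and 5/17 (borrowed from the interim data for scale only): 25 × 0.75 = 18.75, 25 × 8/17 = 11.8 and 25 × 5/17 = 7.4, rounded to 19, 12 and 7. The values of p are also assumptions.

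| Tested, of 25 | n/N | Shown if p = 50% | Shown if p = 75% | Shown if p = 100% |
|---|---|---|---|---|
| 25 | 1.00 | 50% | 75% | 100% |
| 19 | 0.76 | 38% | 57% | 76% |
| 12 | 0.48 | 24% | 36% | 48% |
| 7 | 0.28 | 14% | 21% | 28% |

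With patients assessed as the denominator, each column would show its p in every row.

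**QTcF illustration.** The four ranges in SAP 7.12.4 cover every possible value, so among patients with an ECG they add to 100%. With the set size as denominator they add to n/N: 19/25 = 76% or 12/25 = 48%. A range holding an assumed 10% of patients with an ECG would be shown as 10% × 0.76 = 7.6% or 10% × 0.48 = 4.8%. The safety analysis set is assumed, since the section names none.

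**What is not affected.** SAP 7.11.1 also reports the percentage positive at baseline and at any post-baseline time. Every member of the immunogenicity-evaluable set has a baseline sample and at least one later sample, so n = N and the percentage is right.

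**The case against.** The best defence is that the rule is a general default, worded loosely enough for a programmer to use counts by visit, and that Protocol 13.9 bases the immunogenicity analysis on available data. Neither settles the matter. Protocol 13.9 ties its statement to the safety analysis set, which is not the SAP's immunogenicity set, and gives no denominator by time point. SAP 7.10.1.1 does set requirements on the number of patients and non-missing values at each nominal time for drug concentrations; nothing similar appears for ADA or QTcF.

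The objections to scope stand, and they rule out several stronger readings that a reader might infer:

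- *The secondary ADA endpoint is biased.* It is not: the any-post-baseline incidence has the correct denominator.
- *The interim data already show the distortion, as 6/17 = 35%.* The 6 of 8 is a rate of positivity after treatment, not a C3D1 rate. The 8 patients with ADA data need not be those who reached Cycle 3, and nothing shows that the ADA set would be 17. If those 8 formed the set, 6/8 = 75% would print unchanged.
- *Prolonged QTcF is understated at every later visit.* Scheduled ECGs stop at C2D1 or C3D1 apart from end of treatment. SAP 7.12.4 also summarises the maximum post-baseline value and the change to it, which do not use visit denominators.
- *ADA is the established cause of lost exposure and infusion reactions.* Protocol 4.1.2.1 and 4.3.3 attribute this in monkeys, 4.3.1 calls the human relevance unclear, and the impact in patients is still being explored.
- *Falling percentages will be taken for transient ADA.* This is possible but not certain. Protocol 13.9 plans a direct summary of transient and persistent ADA, and the SAP lists all ADA data. A rising true rate could also offset the decline.

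It is also fair that a denominator of patients assessed is selective if dropout is related to ADA or toxicity. That is a reason to show n, not to count untested patients as if they were negative.

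**Conclusion.** The point holds in this limited form. Applied literally, SAP 7.2 understates the ADA-positive percentage at each time point, and the QTcF category percentages, by the factor n/N wherever results are missing. The direction and the formula follow from the text. The size depends on how many patients are assessed, which the documents do not give for the analysis sets: the drop from 75% to 57%, 36% or 21% rests on an assumed set of 25, an assumed constant positivity and illustrative numbers tested. Within the immunogenicity-evaluable set the loss at early visits should be smaller than among all treated patients, because members must have at least one post-baseline sample.

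The QTcF part is narrow: mainly C2D1 in phase 1b, C2D1 and C3D1 in phase 2, and missed end-of-treatment ECGs. No dose, stopping or efficacy rule uses either table, and Protocol 13.9 describes the immunogenicity analyses as exploratory and descriptive. This is a rule that produces wrong percentages in two descriptive tables. It is worth correcting because the correction is cheap.

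**What to change.** Amend SAP 7.2 to say that, for summaries by visit or time point, the denominator is the number of patients in the analysis set with a non-missing result at that time point, and that this n is displayed. Keep the analysis-set denominator for summaries of occurrence at any time during the study, such as TEAEs and ADA positivity at any post-baseline time. A short cross-reference in SAP 7.11.1 and 7.12.4, with the analysis set for QTcF named in the latter, would remove the remaining doubt.

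The cost is one sentence and a table footnote. The downside is small: the denominator varies by visit and describes only patients still assessed, which displaying n makes visible.

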7.2.1 Data Presentations

Modakafusp alfa Single Agent Dose Escalation: by dose level

Dose Level 1	Dose Level 2	Dose Level 3	Continue for each dose level	Total escalation
--------------	--------------	--------------	------------------------------	------------------

Modakafusp alfa + Pembrolizumab Safety Lead-in: by dose level

Safety Lead-in Dose Level 1	Safety Lead-in Dose Level 2	Continue for each dose level	Total Safety Lead-in
-----------------------------	-----------------------------	------------------------------	----------------------

Modakafusp alfa + Pembrolizumab Dose Expansion: by cohort

Cohort I (Primary Resistance)	Cohort II (Acquired resistance)	Cohort III (Naïve to Prior Anti-PD1)	Total expansion
-------------------------------	---------------------------------	--------------------------------------	-----------------

Total: total_escalation, total safety lead-in, total expansion, total population

Total escalation	Total safety lead-in	Total expansion	Total
------------------	----------------------	-----------------	-------

7.2.2 Definition of Study Days

Study Day 1 is defined as the date on which a subject is administered their first dose of the study drug (excluding test dose if any). Other study days are defined relative to the study Day 1 and the study Day -1 (the day prior to Study Day 1).

7.2.3 Methods for Handling Missing Data

For efficacy and safety data, no imputation of values for missing data will be performed. Imputation rules for incomplete dates are described in Appendix B.

7.3 Analysis Sets

- Safety Analysis Set: The safety analysis set will include all enrolled patients who received at least one dose (even incomplete) of the study drug.
- Response evaluable Analysis set: The response evaluable analysis set is a subset of the safety analysis set including patients with measurable disease at baseline and at least 1 post-treatment evaluation.
- DLT Evaluable Analysis Set: patients who receive all Cycle 1 doses of modakafusp alfa or experience a DLT in Cycle 1 in the dose-escalation portion of the study; or patients who receive all Cycle 1 doses of modakafusp alfa in combination with pembrolizumab or experience a DLT in Cycle 1 in the safety lead-in portion of the study.
- Pharmacokinetic Analysis Set: patients from the safety analysis set who have sufficient data to calculate at least 1 PK parameter for modakafusp alfa.
- Immunogenicity-evaluable Analysis Set: Includes patients with a baseline and at least one post-baseline immunogenicity assessment.

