6.3 Duration of Study

6.3.1 Duration of an Individual Patient's Study Participation

Patients may receive modakafusp alfa as a SA for up to 1 year or in combination with pembrolizumab for up to 2 years. Patients with demonstrated clinical benefit can continue treatment beyond those points if approved by the sponsor. These patients can continue receiving treatment in this study or in any of the poststudy access modalities described in the protocol (Section 6.3.5). Patients may discontinue treatment when they meet any of the discontinuation criteria stated in the protocol (Section 9.6).

All patients will have an EOT visit 30 days (+10 days) after receiving the last dose of study drug or before the start of subsequent systemic anticancer therapy, whichever occurs first, to permit detection of any delayed TEAEs and to resolve any ongoing events. Patients with unresolved TEAEs will continue the periodic safety follow-up until complete resolution or stabilization (established as sequelae) occurs.

Patients who discontinue study treatment for reasons other than progressive disease (PD) will continue PFS follow-up every 12 ± 1 weeks from the EOT visit until the occurrence of PD, lost to follow-up, consent withdrawal, death, start of subsequent systemic anticancer therapy, or study termination, whichever occurs first. After disease progression or starting another systemic anticancer therapy, all patients will be followed every 12 ± 1 weeks for OS until death or study termination.

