 - Grade 3 diarrhea that can be controlled to Grade < 3 in ≤ 3 days with appropriate treatment.
 - Any other Grade 3 TEAE for which NCI CTCAE v5 Grade 4 or 5 does not exist or the NCI CTCAE does not consider the AE Grade 4 to be life-threatening.
- Any Grade 2 nonhematologic toxicity that is considered by the investigator to be related to study drug and dose-limiting.

In the dose escalation phase, DLTs are defined as events meeting the criteria above that occur before Cycle 2 Day 1 administration. TEAEs meeting DLT definitions occurring in later cycles or during expansion will determine the suitability of the MTD as the RP2D.

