9.4 Completion of Study (for Individual Patients)

Patients will be considered to have completed the study if they are discontinued from study drug and 1 or more of the following situations occur:

- Death.
- Consent withdrawal.
- Investigator decision.
- Study terminated by the sponsor.
- Lost to follow-up.
- Transfer of patient to a long-term safety study or similar program.

The consequence of consent withdrawal is that no new information will be collected from the withdrawn patient and added to the existing data or any database.

Once study has been completed, all study procedures outlined for the end of study visit will be completed as specified in the SOE ([Appendix A](#)). After study completion, no new information will be collected from the completed patient and added to the existing data or any database.

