10.3 Monitoring of AEs and Period of Observation

AEs, both nonserious and serious, will be monitored throughout the study as follows:

- AEs will be reported from the signing of informed consent through 30 days after administration of the last dose of study drug or the start of subsequent anticancer therapy, whichever occurs first, and recorded in the eCRFs. The reporting period for irAEs (Section 8.6.3.2) is extended to 90 days after administration of the last dose of study drug or the start of subsequent anticancer therapy, whichever occurs first, and recorded in the eCRFs.
- SAEs will be reported to the Takeda Global Pharmacovigilance department or designee from the signing of informed consent through 30 days after administration of the last dose of study drug, even if the patient starts nonprotocol therapy, and recorded in the eCRF. The reporting period for serious irAEs is extended to 90 days after administration of the last dose of study drug. After this period, only related SAEs must be reported to the Takeda Global Pharmacovigilance department or designee. SAEs should be monitored until they are resolved or are clearly determined to be caused by a patient's stable or chronic condition or intercurrent illness(es).

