Starting from the second dose level, the BLRM with overdose control will be used for all subsequent dose escalation recommendations. The BLRM recommended dose at the end of each dosing cohort will be that which has the highest posterior probability of having a DLT rate that is ≥ 0.16 and ≤ 0.33 . Following the EWOC principle, the posterior probability of the recommended dose having a DLT rate above 0.33 must not exceed 35%. Escalation will continue until one of the following stopping rules is met before reaching the maximum number of patients:

- At least 6 patients are enrolled at the current dose, the current dose is the BLRM recommended dose for the next group of patients, and the observed DLT rate is $\leq 33\%$, OR
- If the next recommended dose is a tested dose and has already enrolled 9 patients, the BLRM posterior probability of the next recommended dose having a DLT rate that falls into the interval $[0.16, 0.33)$ exceeds 50%, and the observed DLT rate is $\leq 33\%$.

Once either of the above rules has been met, MTD may be declared. Alternative stopping rules may also be considered following discussions between the sponsor and the investigators.

The description and operating characteristics of the BLRM for dose escalation are included in Appendix C.

Posterior probability of under-toxicity $[0,0.16)$, target toxicity $[0.16,0.33)$, and over-toxicity $[0.33,1]$ will be summarized in the CSR based on all the data in the dose escalation phase for patients in DLT-evaluable set.

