All summaries will be by dose levels by phases (escalation, safety lead-in, and expansion) for patients in the safety analysis set.

Patients with the same AE more than once will have that event counted only once within each body system, and once within each preferred term. Patients with the same AE more than once will have the maximum intensity of that event counted once within each body system, and once within each preferred term.

Most commonly reported (at least 10% of all patients in each phase or overall population as appropriate) treatment-emergent AEs will be presented by preferred term only. Patients with the same AE more than once will have that event counted only once within each preferred term.

An overall summary TEAE table will include numbers and percentages of patients who had any TEAE, and qualified TEAEs: drug-related AE, not drug-related AE, grade 3 or higher TEAE, grade 3 or higher drug-related AE, serious AE (SAE), drug-related SAE, not drug-related SAE, SAEs leading to study drug discontinuation, AEs resulting in study drug discontinuation, and on-study deaths. On-study death is defined as deaths that occur between the first dose of study drug and up to 30 days after the last dose of study drug and deaths assessed related to study drug that occur 30 days after the last dose of study drug.

Most frequent, >5% of all patients in each phase or overall population as appropriate, non-serious TEAE will be presented by system organ class and preferred terms for clinical trial disclosure.

A by-patient listing of DLTs that occur during Cycle 1 of treatment will be presented by dose levels for all patients in the DLT evaluable set. Patients will be grouped by the dose level to which they were originally assigned, including those who receive subsequent treatment at a lower or higher dose level.

A by-patient listing of all deaths regardless of whether on study or not will also be presented. In this listing, on-study deaths will be flagged.

Adverse Events of Special Interest (AESI)

For modakafusp alfa, infusion-related reactions (IRRs) are designated as AESIs.

For pembrolizumab, the following AEs are considered AESIs:

- Pneumonitis.
- Hepatitis.
- Colitis.
- Nephritis.
- Dermatologic reactions.
- Myocarditis.
- IRR.
- Endocrinopathies, including thyroid disorders, adrenal insufficiency, type 1 diabetes mellitus, and hypophysitis.

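### The SAP's DLT-evaluable set requires Cycle 1 dosing but not completed DLT observation, so the CSR toxicity posterior can count early leavers as non-events

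*SAP*

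**What the plan says.** SAP 7.3 admits to the DLT-evaluable set "patients who receive all Cycle 1 doses of modakafusp alfa or experience a DLT in Cycle 1 in the dose-escalation portion of the study". The safety lead-in limb has the same form: "patients who receive all Cycle 1 doses of modakafusp alfa in combination with pembrolizumab or experience a DLT in Cycle 1 in the safety lead-in". Neither limb states how long a patient must be observed. Protocol 13.2 defines no DLT set.

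Two outputs use the set. SAP 7.1 says the posterior probabilities of under-, target and over-toxicity will be "summarized in the CSR based on all the data in the dose escalation phase for patients in DLT-evaluable set". SAP 7.12.1 adds a "listing of DLTs that occur during Cycle 1 of treatment will be presented by dose levels for all patients in the DLT evaluable set".

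Protocol 8.2 sets the escalation window: "In the dose escalation phase, DLTs are defined as events meeting the criteria above that occur before Cycle 2 Day 1 administration". Protocol 6.1.1 runs DLT assessment until Cycle 2 Day 1 can safely be given. Protocol 9.5 replaces escalation patients who stop during Cycle 1 for a reason other than a DLT.

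On follow-up after stopping, protocol 6.3.1 says "All patients will have an EOT visit 30 days (+10 days) after receiving the last dose of study drug", or before new systemic therapy if that comes first. Protocol 10.3 collects AEs "through 30 days after administration of the last dose of study drug or the start of subsequent anticancer therapy, whichever occurs first"; SAEs are reported for the 30 days even if new therapy starts. Protocol 9.4 adds: "The consequence of consent withdrawal is that no new information will be collected from the withdrawn patient".

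**The concern.** Being free of DLTs is informative only if the patient was watched for the period in which a DLT could occur. SAP 7.3 tests dosing, and with one infusion per cycle that test is passed on Day 1. A patient lost in the first week without a DLT carries the same weight as one followed to Cycle 2.

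The replacement rule sharpens this. Protocol 9.5 treats an early non-DLT discontinuation as not good enough to fill a place in the cohort, yet SAP 7.3 keeps that patient, so the patient and the replacement can both sit in the denominator. At stake is the planned statistical summary of escalation toxicity in the CSR, which would look somewhat safer than the data support.

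**Working it through.** **1. Doses in Cycle 1.** Dosing is every 3 weeks in a 21-day cycle (protocol 2.0 and 6.1.1), and Table 16.a shows one Cycle 1 infusion, on Day 1. Receiving all Cycle 1 doses therefore means receiving that infusion.

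**2. Observation needed.** The next dose is due on Day 1 + 21 = Day 22. One DLT criterion in protocol 8.2, a Cycle 2 delay of more than 14 days, can be met only after Day 22 + 14 = Day 36. Section 8.2 speaks both of Cycle 1 and of the time before Cycle 2 Day 1 administration, while 6.1.1 runs until that dose can be given. The three do not agree on when the window closes for a patient who never receives Cycle 2.

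**3. Who is affected.** After a single Day 1 dose, AE collection runs to Day 1 + 30 = Day 31, beyond Day 22. Patients who merely stop treatment are therefore normally still observed. The gap concerns those who withdraw consent, are lost, or start new anticancer therapy (non-serious AEs only).

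**4. How they enter the posterior.** The model in SAP Appendix C is a binary logistic regression with no weighting for partial follow-up, and SAP 7.2.3 rules out imputing missing safety data. A set member without a recorded DLT then contributes a factor (1 − π) to the likelihood, where π is the DLT rate at that dose. This factor falls as π rises. Compared with leaving the patient out, it cannot raise the posterior probability of over-toxicity at that dose, whatever the prior.

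**5. Size.** The plan gives no figure to reproduce. Let p be the true DLT rate, d the share leaving observation early and f the share of their DLT risk captured before they leave. Leaving is assumed independent of DLT risk.

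- Current set: p[1 − d(1 − f)]. Error: −pd(1 − f), never positive.
- Completed-observation set (DLT, or full observation): [p(1 − d) + dpf] / [(1 − d) + dpf]. Error: dpf(1 − p) / [(1 − d) + dpf], never negative.

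With p = 0.33, the upper limit of the target interval, and assumed d and f:

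| d | f | Current set (error) | Completed-observation set (error) |
|---|---|---|---|
| 0.10 | 0.9 | 0.3267 (−0.0033) | 0.3514 (+0.0214) |
| 0.30 | 0.9 | 0.3201 (−0.0099) | 0.4057 (+0.0757) |
| 0.10 | 0.5 | 0.3135 (−0.0165) | 0.3421 (+0.0121) |
| 0.30 | 0.5 | 0.2805 (−0.0495) | 0.3742 (+0.0442) |

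First row: 0.33 × (1 − 0.10 × 0.1) = 0.3267, and (0.297 + 0.0297) / (0.90 + 0.0297) = 0.3514.

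With f = 0 the current set reads 0.297 (d = 0.10) or 0.231 (d = 0.30) and the other set reads 0.330. That case is unlikely, since Table 16.a has Cycle 1 visits on Days 2, 3, 4, 8 and 15.

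**The case against.** The strongest reply is that little depends on this set. The documents do not tie live escalation decisions or the primary count of patients with DLTs to it; cohorts are sized in evaluable patients and early non-DLT discontinuations are replaced. Against the plan's own DLT counts the loss is small. SAP Appendix C, Table 3 expects at most 3.9 DLTs per study, so expected missed DLTs, 3.9 × d × (1 − f), run from 0.04 (d = 0.10, f = 0.9) to 0.59 (d = 0.30, f = 0.5). All of this stands and keeps the point minor.

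Three narrower objections also stand. A patient whose only infusion was cut short may not have received all Cycle 1 doses, so the set is met on Day 1 only when the infusion is fully given. Entry as a non-event is an inference, because the SAP does not say how incomplete follow-up is coded. SAP 7.4 and Appendix A already tabulate and list analysis populations and discontinuation reasons, so only observed time and the comparison between sets are new.

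Four stronger readings are tempting and not supported:

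- **That the 17.6% who had left the study (protocol 4.3.2.2) is the loss rate.** It is 3 of 17 patients at an interim cutoff, at any cycle and without reasons given. It says nothing specific about the DLT window.
- **That escalation or the overdose limit is compromised.** The 35% limit governs dose recommendations, and the prior parameters and reference dose needed to recompute a posterior are not given.
- **That the lead-in dose decision is affected.** The posterior summary uses escalation data only; the lead-in limb reaches no further than the DLT listing.
- **That the completed-observation set is simply the right one.** It keeps early leavers who had a DLT and drops those who did not. At 90% capture its error is larger than the current one, and at 50% the two are similar.

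**Conclusion.** The wording gap is certain: SAP 7.3 has no observation condition, a CSR summary is computed on the set, and the set keeps patients whom protocol 9.5 replaces. Its direction is downward, given the inference that set members without a DLT count as non-events. Its size is unknown. It is zero if no one leaves observation early. For a true rate of 0.33 and assumed losses of 10% to 30%, it is 0.003 to 0.010 at 90% capture and 0.017 to 0.050 at 50% capture.

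A reader might conclude that the dose selected in phase 1b is unsafe or that the DLT endpoint is biased. The documents do not support that, because the consequence is confined to one descriptive summary. If leaving is independent of DLT risk, the current and completed-observation sets bracket the true rate and neither alone is unbiased. If leaving depends on emerging toxicity, the bracketing is no longer assured. Minor, and worth correcting because it is cheap.

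**What to change.** In SAP 7.3, define DLT-evaluable as a DLT within the window, or planned Cycle 1 dosing plus DLT observation completed to the end of the window, whether or not treatment continues. Apply the same wording to the lead-in limb.

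Reconcile protocol 6.1.1 and 8.2 on when the window ends for a patient who never receives Cycle 2 Day 1, and reconcile the set with the replacement rule in protocol 9.5, so that it is clear whether a replaced patient remains in it.

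In SAP 7.1, present the CSR posterior on both this set and the current all-dosed set, neither labelled as a mere sensitivity check. List the number of patients who differ between the sets, with their reasons and observed time.

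The cost is one reworded definition, one extra table and a short listing. The downside is that the completed-observation posterior is conservative: for a true rate of 0.33 it overstates by about 0.02 to 0.08 at 90% capture under the assumed losses, which is why both must be shown.
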